9.2.1 ITP-specific autoantibodies

The following ITP-specific autoantibodies will be measured using the indirect MAIPA method and pre-chloroquine minus post chloroquine treated scores for PIFT

■ [REDACTED]

■ [REDACTED]

■ [REDACTED]

The results will be expressed in the form of the OD value and for indirect PIFT method using the following categories: 0 = negative; 0.5 = week positive; 1 = positive; 2 = positive; 3 = strong positive; 4 = strong positive.

ITP-specific autoantibodies (OD value and PIFT categories) will be listed by dose arm and timepoint. OD values that are ALD will be displayed as such in the listings.

Descriptive summaries (including n, arithmetic mean, median, SD, minimum and maximum) will be presented by dose arm and visit for absolute values only. Any values that are ALD will be handled as described in [Section 4.2.3](#) for the calculation of the descriptive statistics.

Mean values will be plotted over time by dose arm with all dose arms overlaid on the same plot and separate plots for each variable. In addition, combined individual (spaghetti) plots will be plotted over time by dose arm for each variable (absolute values only). All subjects within each dose arm will be overlaid on the same plot.

In order to evaluate the relationship between changes in platelet count and total IgG, IgG subclasses and ITP-specific autoantibodies the following figures will be presented:

- Spaghetti plot of individual ITP-specific autoantibodies and platelet counts (measured by ACM Global Central Laboratory) will be displayed graphically over time (Day 1 to Day 85 for Dose Arm 1; Day 1 to Day 71 for Dose Arm 2; Day 1 to Day 64 for Dose Arm 3 and Day 1 to Day 57 for Dose Arms 4 and 5) for each subject (linear scale). The ITP-specific autoantibodies [REDACTED] and platelet counts will be overlaid on the same plot (discrete y-axes) with separate plots for each subject (4 lines per plot)

- A scatter plot of platelet counts (measured by ACM Global Central Laboratory) versus ITP-specific autoantibodies measured at the same visit will be presented in linear scale, with separate plots for each dose arm and for each variable [REDACTED]. All subjects and visits will be included on the same plot for each dose arm
- Individual ITP-specific autoantibodies and total IgG (from ACM Global Central Laboratory) will be displayed graphically over time (Day 1 to Day 85 for Dose Arm 1; Day 1 to Day 71 for Dose Arm 2; Day 1 to Day 64 for Dose Arm 3 and Day 1 to Day 57 for Dose Arms 4 and 5) for each subject (linear scale). The ITP-specific autoantibodies [REDACTED] and total IgG will be overlaid on the same plot (discrete y-axes) with separate plots for each subject (4 lines per plot). These plots will be repeated for each of the IgG subclasses.

The plots versus time will include 2 y-axes with the ITP-specific autoantibodies on the left hand y-axis and the platelet counts (or total IgG and IgG subclasses) on the right hand y-axis. Only patients with positive ITP-specific autoantibodies will be described.

All analyses described in this section will be performed on the FAS.

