2.2.3.2 Pharmacodynamic variables

The PD variables are:

- Minimum value and maximum decrease from Baseline in total IgG concentration (absolute and percentage) measured by ACM Global Central Laboratory
- Value and change from Baseline (absolute and percentage) in total IgG concentrations (measured by ACM Global Central Laboratory) to each visit in the Dosing Period and in the Observation Period up to Day 85 in Dose Arm 1, up to Day 71 in Dose Arm 2, up to Day 64 in Dose Arm 3 and up to Day 57 in Dose Arms 4 and 5
- ITP-specific autoantibodies in serum [REDACTED] over time, measured at Day 1, Day 36 and Day 85 in Dose Arm 1, at Day 1, Day 22 and Day 71 in Dose Arm 2, at Day 1, Day 15, and Day 64 in Dose Arm 3 and at Day 1, Day 8 and Day 57 in Dose Arms 4 and 5
- Change from Baseline in IgG subclass concentrations (measured by ACM Global Central Laboratory) to each visit in the Dosing Period and in the Observation Period up to Day 85 in Dose Arm 1 and up to Day 71 in Dose Arm 2, up to Day 64 in Dose Arm 3 and up to Day 57 in Dose Arms 4 and 5

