3.3 Definition of Baseline values

Baseline will be the last available predose value prior to the first infusion of UCB7665, or if missing, the latest non missing value prior to Baseline (screening value or unscheduled visit value).

Measurement-specific Baseline timepoints (based on the scheduled or unscheduled measurements) are presented in [Table 3–1](#).

Table 3–1: Definition of Baseline

Measurement	Definition of Baseline

Safety data:
 
 Clinical chemistry (including proteins) Hematology (including platelets measured locally) Coagulation Urinalysis Vital signs 12-lead ECG Serum safety biomarkers [REDACTED] 	
 Predose Day 1 or if missing the latest non missing value prior to Day 1

Efficacy variables:
 
 Platelets (measured by ACM Global Central Laboratory) ITP bleeding scale NFI-MS 	
 Platelets: Predose Day 1 or if missing the latest non missing value prior to Day 1 ITP bleeding scale: Predose Day 1 or if missing the latest non missing value prior to Day 1 NFI-MS: Predose Day 1

Pharmacodynamic variables:
 
 Total IgG IgG subclasses ITP-specific autoantibodies in serum [REDACTED] 	
 Total IgG: Predose Day 1 or if missing the latest non missing value prior to Day 1 IgG subclasses: Predose Day 1 or if missing the latest non missing value prior to Day 1 ITP-specific autoantibodies: Predose Day 1

Immunological variables:
 
 Immunoglobulins (IgA, IgE and IgM) B- and T-lymphocytes Serum (C3 and C4) and plasma complement (C3a and C5a) ADA Serum BAFF Cytokines, if applicable (as outlined in the protocol) 	
 Predose Day 1 (except B- and T-lymphocytes) B- and T-lymphocytes: Predose Day 1 or if missing the latest non missing value prior to Day 1

ADA=anti-drug antibody; BAFF= B cell activating factor; ECG=electrocardiogram; Ig=immunoglobulin; ITP=primary immune thrombocytopenia; NFI-MS= Neurological Fatigue Index for Multiple Sclerosis; [REDACTED]

If a measurement is repeated at Baseline and is obtained prior to receiving the first dose of UCB7665, then the last available measurement will be used as the Baseline value.

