3.9 Changes to protocol-defined analyses

The protocol stated that changes from Baseline would be evaluated for the ITP-specific autoantibodies. However, as these data are semi-quantitative, changes from Baseline are not considered an appropriate way to present the results and would not provide any additional information. Thus, only absolute values over time will be reported.

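### SAP Section 9.2.1 limits autoantibody results to positive patients without saying when, by which assay or at what cut-off, and plans no group output that shows within-subject loss

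*SAP*

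**What the plan says.** Section 9.2.1 covers two kinds of result: OD values from the MAIPA assay and PIFT scores on the scale "0 = negative; 0.5 = week positive; 1 = positive; 2 = positive; 3 = strong positive; 4 = strong positive". For the tables it says "Descriptive summaries (including n, arithmetic mean, median, SD, minimum and maximum) will be presented by dose arm and visit for absolute values only". Means are also plotted over time by dose arm. Both OD and PIFT results are listed, and Section 9.2 puts the pharmacodynamic listings on the Safety Set.

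The section then plans spaghetti plots that overlay every subject in an arm, and a scatter plot against platelet count that uses every subject and visit. At the end of the paragraph on the axes of the time plots comes "Only patients with positive ITP-specific autoantibodies will be described", followed by "All analyses described in this section will be performed on the FAS".

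Section 3.9 explains why the protocol's change from Baseline is dropped: "as these data are semi-quantitative, changes from Baseline are not considered an appropriate way to present the results". It concludes "Thus, only absolute values over time will be reported". Table 3-1 in Section 3.3 does define a Baseline, "ITP-specific autoantibodies: Predose Day 1", but the restriction to positive patients does not refer to it. Section 2.2.3.2 sets three assessments per subject, for example "measured at Day 1, Day 36 and Day 85 in Dose Arm 1".

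**The concern.** The restriction decides who is summarized, and it can be programmed in at least three ways: positive at Baseline, positive at any visit, or positive at the visit being summarized. The last of these selects on the post-dose result. A subject who turns negative after dosing would drop out of that visit's mean and median, and only the remaining positives would be described.

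No group summary would correct this. Change from Baseline has been removed, and 9.2.1 plans no shift table and no count of subjects who go from positive to negative. The reason given for removing change from Baseline is that the data are semi-quantitative. That reason applies equally to the arithmetic mean and SD, which stay.

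Autoantibodies over time are a listed pharmacodynamic variable (Section 2.2.3.2), and their relationship to platelet change is an exploratory objective (Section 2.1.3). What is at stake is whether the report shows fairly what happens to the autoantibody on treatment.

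**Working it through.** The SAP gives no sample size, power or cut-off for autoantibodies, so there is no figure of its own to reproduce. The check compares the texts and then runs two illustrations on assumed data.

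**Who is included.**

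| Place in SAP | Population stated |
|---|---|
| 9.2.1, restriction sentence | positive patients; time, assay and OD cut-off not given |
| 9.2.1, spaghetti plots by arm | all subjects in the arm |
| 9.2.1, scatter plot | all subjects and visits |
| 9.2.1, closing line | FAS, no subset named |
| 9.2, listings | Safety Set |
| 6.2, Baseline characteristics | Safety Set, no positivity limit |

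The restriction and the two all-subjects plots cannot both hold if the restriction covers the whole section. The log for SAP Amendment 2 (Section 14.2.2, Change #15) records the sentence as added at the end of 9.2.1, which fits section-wide scope. Its place in the current text, after the axes of the time plots, fits a narrower one. Section 9.3.4 shows that the SAP can settle such questions: for anti-drug antibodies it defines positivity at Baseline, treatment-emergent positivity and overall status.

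**Illustration 1, OD (all values assumed).** Ten Baseline-positive subjects start at OD 1.0. Of these, k fall to 0.1, taken as negative, and the other 10 − k fall to 0.6, taken as positive.

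- All ten kept: mean = [0.1k + 0.6(10 − k)] / 10.
- Only those positive at the visit: mean = 0.6(10 − k) / (10 − k) = 0.6.

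| k | Mean, all ten kept | Fall | n, visit-positive | Mean, visit-positive | Fall shown |
|---|---|---|---|---|---|
| 2 | 0.50 | 50% | 8 | 0.60 | 40% |
| 5 | 0.35 | 65% | 5 | 0.60 | 40% |
| 8 | 0.20 | 80% | 2 | 0.60 | 40% |

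The visit-positive median is also 0.6 in every row, so reporting a median does not cure the selection. In the last row n is 2. By Section 3.1 the table would then give only n, minimum and maximum.

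**Illustration 2, PIFT scores (all values assumed, and supposing the scores are averaged).** Eight Baseline-positive subjects score 0.5, 1, 1, 2, 2, 3, 3 and 4. The sum is 16.5 and the mean 16.5/8 = 2.06. The weakest scores fall to 0 and the rest do not change.

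| Lost | Visit-positive mean | Baseline-positive mean (n = 8) |
|---|---|---|
| 2 | 15/6 = 2.50 | 15/8 = 1.88 |
| 4 | 12/4 = 3.00 | 12/8 = 1.50 |
| 6 | 7/2 = 3.50 | 7/8 = 0.88 |

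Under the visit-by-visit reading the mean rises while autoantibodies are being lost. If losses were unrelated to score, the visit-positive mean would stay at about 2.06 on average, whatever the number lost. The only trace in the table is the falling n.

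**Subject-level readings.** If positive means positive at Baseline, the same subjects appear at every visit and the fall is visible. If it means positive at any visit, Baseline-negative subjects who become positive are added, but nobody who loses the autoantibody is removed.

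**The case against.** A reader might infer that the plan hides the pharmacodynamic effect. The documents do not support that. The sentence speaks of patients rather than results, which reads naturally at subject level, and then no one who turns negative is removed. It may also govern only the individual time plots, where it merely selects which subjects get a plot and nothing is averaged. Both points stand as possible readings. The text does not choose between them and the broader ones, and that is the defect.

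A reader might also infer that results appear only as arithmetic means. That is wrong: median, minimum and maximum are planned in the tables, the Safety Set listings keep each subject's course, and individual plots are planned, although the restriction may reach those plots.

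Nor is it established that PIFT scores will be averaged. The SAP calls them categories and says explicitly only that they are listed. Section 3.1 provides counts and percentages for categorical variables. The names of the plotted variables are blacked out. On the other hand, the table sentence in 9.2.1 does not exempt PIFT, so this needs stating.

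The magnitudes are assumed, and the constant 40% follows from the chosen inputs. Finally, the variable serves an exploratory objective. The secondary pharmacodynamic objective is total IgG, and no test rests on autoantibodies. All of this limits the size of the point. None of it supplies the missing definition or a group output for within-subject loss.

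**Conclusion.** The point holds in a limited form. Positivity is undefined in time, assay and OD cut-off in the readable text, and the restriction conflicts with the plots that include all subjects unless its scope is narrowed. Masking of a fall is possible only if positivity is applied visit by visit. The SAP neither adopts nor excludes that reading.

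Independently of that reading, Section 3.9 and Section 9.2.1 do not fit together: change from Baseline is rejected as unsuitable for semi-quantitative data, while arithmetic means remain. As a result, only listings and individual plots can show a subject losing the autoantibody.

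The sizes given (40% shown against 50% to 80%, or a mean rising from 2.06 to 3.50) rest wholly on assumed scores and the visit-by-visit reading. They show the direction of a possible error and do not predict its size. The change is worth making, but the stakes are small.

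**What to change.** In Section 9.2.1, replace the restriction with a definition: summaries over time include subjects positive at Baseline (predose Day 1) for the given antigen and assay, by the laboratory's stated cut-off, and keep them at every later visit whatever the later result.

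Then:

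- State which tables and figures the restriction covers, and reconcile it with the spaghetti and scatter plots that take in all subjects.
- Add a Baseline-to-visit shift table by dose arm for the two post-dose assessments, including Baseline-negative subjects who become positive.
- Summarize PIFT by number and percentage in each category instead of mean and SD.
- For OD, rely on the median and range already planned.

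The cost is a few sentences of SAP text, one added table and a change of statistic in existing outputs. No new data are needed.

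A shift table suits semi-quantitative data and shows within-subject movement without subtracting scores, so it respects the reason given in Section 3.9.

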9.2.2 Total IgG and IgG subclasses

Total IgG concentrations (measured by ACM Global Central Laboratory) and IgG subclasses will be listed by dose arm and visit including changes from Baseline and percentage changes from Baseline. Descriptive summaries (including n, arithmetic mean, median, SD, minimum and maximum) will be presented by dose arm and visit for absolute values, changes from Baseline and percentage changes from Baseline. The maximum decrease from Baseline in total IgG (absolute and percentage decrease) will be reported in the listing and summarized for each dose arm based on the results obtained from ACM Global Central Laboratory. Summary tabulations (for total IgG only) by dose arm will be repeated for the subgroups defined in [Section 4.8](#).

In the event that a decrease from Baseline in total IgG is not observed in a given subject, the maximum decrease will be reported as the smallest increase from Baseline.

Mean, median, median change from Baseline and mean and median percentage change from Baseline values in total IgG (measured by ACM Global Central Laboratory) will be plotted over time by dose arm with all dose arms overlaid on the same plot. Additional figures will be presented in conjunction with the ADA results as described in [Section 9.3.4](#) as well as figures in conjunction with the platelet results as described in [Section 8.1.1](#).

Finally, a separate figure will be presented by subject showing the individual total IgG results from ACM Global Central Laboratory.

Any values that are BLQ or ALQ will be handled as described in [Section 4.2.3](#).

All analyses described in this section will be performed on the PD-PPS. In case rescue medications are taken, only the IgG data up to the start date of rescue medication will be utilized for the summary tables. Listings will contain all the data but a footnote will be included indicating the patients for which some data has been excluded from the summary tables. In case of partial dates, the imputation rules for partial dates described in [Section 4.2.7](#) will be applied.

9.3 Other immunological variables

The analysis of the immunological data will be performed on the FAS. All listings will be presented for the SS.

9.3.1 Serum immunoglobulins and lymphocytes

Serum immunoglobulins (IgA, IgE and IgM) will be listed by dose arm and visit including changes from Baseline. Descriptive summaries (including n, arithmetic mean, median, SD, minimum and maximum) will be presented by dose arm and visit for both absolute values and changes from Baseline. The listing and summary tabulation will be repeated for B- and T-lymphocytes.

Mean and mean change from Baseline values will be plotted over time by dose arm with all dose arms overlaid on the same plot and separate plots for each variable (IgA, IgE, IgM, B- and T-lymphocytes).

Similar plots will be presented by dose arm for the mean and mean change from Baseline values in IgA, IgE, IgM and total IgG only. Separate plots will be presented for each dose arm with all variables overlaid on the same plot.

In addition, individual immunoglobulin (IgA, IgE, IgM and total IgG) values will be graphically displayed over time with all variables overlaid on the same plot and separate plots for each subject.

For all overlaid plots for the immunoglobulin variables, discrete y-axes may be used for applicable variables to accommodate changes in the scale of measurement.

Any values are that BLQ or ALQ will be handled as described in [Section 4.2.4](#).

All analyses described in this section will be performed on the FAS.

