3.5.3 Full Analysis Set

The Full Analysis Set (FAS) will consist of all subjects who have received at least 1 infusion (full infusion) of UCB7665 and, in addition, have a Baseline and at least 1 post-Baseline measurement for platelet count (measured by ACM Global Central Laboratory).

The analysis of the PD (excluding total IgG and IgG subclasses), efficacy and immunologic variables will be performed on the FAS. Efficacy analyses will be repeated for the pharmacodynamics per protocol set (PD-PPS) where stated in the SAP.

Platelet data for subjects who have taken rescue medications (based on medical review and defined in Section 8.1.4) will only be utilized in the summary tables up to the start of these rescue medications.

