3.5.6 Pharmacodynamic Per Protocol Set

The Pharmacodynamic Per Protocol Set (PD-PPS) is a subset of the FAS, consisting of those subjects who had no important protocol deviations potentially affecting the serum concentration of total IgG, as confirmed during a pre-analysis review of the data prior to database lock. Protocol deviations may not necessarily lead to total exclusion of a subject from the PD-PPS but may lead to exclusion of specific data.

The PD-PPS will be used for the analysis of the total IgG and IgG subclasses.

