8.1 Platelets

All efficacy analyses are based on platelet count measured by ACM Global Central Laboratory. Measurements of platelet count obtained by the local laboratory will be listed and summarized as part of the safety laboratory data. These are not included in the analyses described in the sections below. All tabulations and mean figures will be presented for both the FAS and the PPS unless otherwise stated. Median figures and individual figures will be presented for the FAS only. In case rescue medications are taken, only the platelet data up to the start date of rescue medication will be utilized for the summary tables (refer to [Section 8.1.4](#)). In case prohibited medications

affecting platelets are taken, only the platelet data up to the start date of prohibited medication will be utilized for the summary tables for the PPS (refer to Section 3.4). Listings will contain all the data but a footnote will be included indicating the patients for which some data has been excluded from the summary tables. In case of partial dates, the imputation rules for partial dates described in Section 4.2.7 will be applied.

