8.1.4 Rescue medication definition (after medical inspection)

In the rescue medication section of the protocol, rescue medication is defined as platelet substitution or treatment with a commercially available IVIg. In addition, the prohibited medications PLEX, dexamethasone and rituximab will also be considered as a rescue medication for analysis.

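### The rescue cut-off is not applied to most PD and immunological outputs, and Section 9.3.1 plots mean total IgG on the FAS although the SAP assigns it to the PD-PPS

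*SAP*

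**What the plan says.** **What counts as rescue.** SAP 8.1.4 reports that in the protocol "rescue medication is defined as platelet substitution or treatment with a commercially available IVIg". It adds that "the prohibited medications PLEX, dexamethasone and rituximab will also be considered as a rescue medication for analysis".

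**Where the cut-off applies.** In 3.5.3 it is written for platelet data of rescued subjects, which "will only be utilized in the summary tables up to the start of these rescue medications"; 8.1 repeats this. Sections 8.1.3.3 and 8.2.1.1 apply it to the data behind their own tables, which include bleeding data. Section 9.2.2 says that "only the IgG data up to the start date of rescue medication will be utilized for the summary tables".

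**Where it is absent.** Sections 9.2.1 (autoantibodies), 9.3.1 (IgA, IgE, IgM, B- and T-lymphocytes), 9.3.2 (complement) and 9.3.3 (serum biomarkers and BAFF) have no rescue rule, and each places its analyses on the FAS. For the scatter of platelets against autoantibodies, 9.2.1 says: "All subjects and visits will be included on the same plot for each dose arm".

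**Which set total IgG belongs to.** Section 3.5.6 says: "The PD-PPS will be used for the analysis of the total IgG and IgG subclasses". Section 3.5.3 excludes total IgG and subclasses from the PD variables analysed on the FAS, 9.2 repeats the exception, and 9.2.2 puts all its analyses on the PD-PPS. Section 9.3.1 nevertheless says: "Similar plots will be presented by dose arm for the mean and mean change from Baseline values in IgA, IgE, IgM and total IgG only". It closes by placing everything in the section on the FAS.

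**The concern.** There are two separate problems.

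First, the SAP already declines to summarise total IgG and subclasses after rescue, but it does not extend that to closely related variables. The exploratory objectives in 2.1.3 name IgG subclasses, IgM, IgA, IgE and complement together, yet only the subclasses are cut. Treatments that 8.1.4 counts as rescue can be expected on general pharmacological grounds to act on these variables: plasma exchange on circulating antibodies, rituximab on B cells, IVIg on measured antibody. Their effects would be described by dose arm as if they belonged to UCB7665. The scatter in 9.2.1 serves the objective on platelet count and autoantibodies. A post-rescue point can carry a raised count and a lowered autoantibody value, both due to the rescue treatment.

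Second, total IgG change is a secondary objective (2.1.2). A mean-change plot on a different analysis set from the table for the same variable invites conflicting readings in the study report.

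**Working it through.** The SAP states no figure on this point, so there is none to reproduce. The check compares the current rules section by section.

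| Variable | Section | Set | Cut-off in tables | Cut-off in figures |
|---|---|---|---|---|
| Total IgG, subclasses | 9.2.2 | PD-PPS | Yes | Not stated |
| Total IgG mean and mean-change plots | 9.3.1 | FAS | n/a | None |
| Autoantibodies | 9.2.1 | FAS | None | None; scatter takes all subjects and visits |
| IgA, IgE, IgM, lymphocytes | 9.3.1 | FAS | None | None |
| Complement | 9.3.2 | FAS | None | None |
| BAFF and other biomarkers | 9.3.3 | FAS | None | None |

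**Could the FAS definition supply the missing cut-off?** No. The rescue sentence in 3.5.3 limits platelet data only.

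**Do the two IgG sets differ in content?** By 3.5.6 the PD-PPS is a subset of the FAS. It leaves out subjects, or specific data, with important deviations that may affect total IgG. Section 8.1.4 calls PLEX, dexamethasone and rituximab prohibited, so data removed from the PD-PPS on that ground could return in the 9.3.1 curves. If any total IgG data are excluded, the 9.3.1 mean and the 9.2.2 mean for that arm rest on different data.

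**Other total IgG plots.** Section 8.1.2 also plots mean, median and change in total IgG by arm, under 8.1, where mean figures are for the FAS and PPS. No rescue cut-off is stated for those IgG figures either.

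**Size, as illustration only.** Arm sizes come from 2.4: 15 in Dose Arms 1 and 2, and 6 to 12 in Dose Arms 3 to 5. The number of rescued subjects, k, is assumed. The share of an arm mean carried by post-rescue values is k/n:

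| k | n=15 | n=12 | n=6 |
|---|---|---|---|
| 1 | 6.7% | 8.3% | 16.7% |
| 2 | 13.3% | 16.7% | 33.3% |
| 3 | 20% | 25% | 50% |

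With one rescued subject, the arm mean moves by d/n, where d is the difference between that subject's value after rescue and what it would have been without rescue. The SAP gives nothing from which d can be obtained.

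**How many visits are exposed.** By 2.2.3.2, autoantibodies are measured on Day 1 and at two later visits, the last being end of study. By 2.2.4, IgA, IgE and IgM are measured after Baseline at the last dosing visit and two observation visits. Few visits are involved, but the final autoantibody sample is the one most likely to follow a rescue. Section 9.2.1 also restricts the description to autoantibody-positive patients, so n there can be below the arm size.

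**The case against.** The strongest reply is that these are descriptive outputs, mostly for exploratory objectives, and that keeping all observed FAS data is a legitimate choice. Concomitant medications are listed with dates (6.4), important deviations are listed (5.2) and individual immunoglobulin plots are produced (9.3.1), so a careful reader could trace a rescued subject. A single set for the isotype overlay in 9.3.1 can also be defended, because its lines then describe the same subjects.

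Much of this stands. It limits the size of the point and shapes the remedy: moving only the IgG line to the PD-PPS would mix sets within one figure. It does not remove the point. The SAP gives no reason for including post-rescue IgM but not IgG subclasses, and a choice of set that 3.5.3, 3.5.6, 9.2 and 9.2.2 contradict is not a stated choice.

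Several stronger readings are tempting but not supported:

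- A reader might infer that the cut-off protects only platelets and IgG in the whole plan. Sections 8.1.3.3 and 8.2.1.1 also cut bleeding-related data.
- A reader might infer that 9.2.2 already cuts its mean IgG figures. Its rule names only the summary tables.
- A reader might infer that the SAP cuts IgG because rescue alters it. That is plausible, but 9.2.2 gives no reason.
- A reader might attach a definite bias to B cells or IgG. That needs an assumed rescue effect and rescue count. A percentage shift would also be on a scale that 9.3.1 does not report, since it summarises absolute values and changes.

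**Conclusion.** The point holds in two parts. Within the PD and immunological variables, only the total IgG and subclass summary tables are cut at rescue; autoantibodies, IgA, IgE, IgM, lymphocytes, complement and BAFF are not. Separately, 9.3.1 contradicts the rest of the SAP on the analysis set for total IgG. The second part needs no assumption. The practical weight of the first depends on how many subjects are rescued and when, which the SAP does not say. At the planned arm sizes, one such subject carries between 6.7% and 16.7% of an arm mean at a visit. The consequence is for interpretation of PD and immunology. No hypothesis test or error rate is touched, and nothing here bears on how patients are managed. The change should be made because the rule already exists and is cheap to extend.

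**What to change.** 1. Apply the rescue cut-off, with rescue as defined in 8.1.4, to the summary tables and mean plots in 9.2.1, 9.3.1, 9.3.2 and 9.3.3, and to the platelet-versus-autoantibody scatter in 9.2.1.
2. State that the 9.2.2 cut-off also covers the mean and median IgG figures, including those in 8.1.2.
3. Keep all data in the listings, and flag post-rescue points in the individual plots.
4. In 9.3.1, present the total IgG mean and mean-change plots on the PD-PPS with that cut-off. Where isotypes are overlaid, use the PD-PPS for every line of that figure.

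The cost is some SAP wording and reuse of a rescue-date flag already needed for platelets and IgG. The downside is slightly fewer late observations in descriptive outputs.
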